#### **Secondary Outcome Measures**

- **Reach: Encounters affected** % clinic encounters where CV Wizard suggests running the full risk assessment tool, i.e., identified a target patient.
- Effectiveness (impact): Patient outcomes 10-year pooled ASCVD risk score change in ASCVD risk score from baseline to last visit of study period (American College of Cardiology-ACC/ American Heart Association - AHA) 10-year pooled ASCVD risk score, 40-75 year olds
- Effectiveness (impact): Patient outcomes last BP ≤140/90 Control of individual CVD risk factors: last BP ≤140/90
- Effectiveness (impact): Patient outcomes last A1c≤8 Control of individual CVD risk factors: last A1c≤8
- Effectiveness (impact): Patient outcomes last LDL<100 Control of individual CVD risk factors: last LDL<100
- Effectiveness (impact): Patient outcomes not current smoker Control of individual CVD risk factors: not current smoker
- Effectiveness (impact): Patient outcomes last BMI ≤25 Control of individual CVD risk factors: last BMI≤25
- Adoption: CDS uptake % of encounters where care team member opts to run the CV
   Wizard risk assessment (explored as both view and print rate and just print rate)
- Implementation: User perceptions Perceived ease of use, usefulness, acceptability of CV Wizard; intent to use it.
- Maintenance over time All measures over 2.5 years of follow-up, Arm 1; 1.5 years, Arm 2.

Table 6. Impact and uptake of the CV Wizard system: Quantitative Measures		
Outcomes, per RE-AIM	Measurement	
Reach:	% clinic encounters where CV Wizard suggests running the full risk assessment tool,	
Encounters affected	i.e., identified a target patient	
Effectiveness (impact):	(i) change in ASCVD risk score (reversible risk; ACC/AHA 10-year pooled ASCVD risk	
Patient outcomes	score, 40-75 year olds; Framingham 30-year CVD risk score, 20-39 year olds).	
	(ii) Control of individual CVD risk factors: last BP ≤140/90; last A1c≤8; last LDL<100;	
	not current smoker; last BMI≤25);	
Adoption: CDS uptake	% of encounters where care team member opts to run the CV Wizard risk	
	assessment	
Implementation: User	Perceived ease of use, usefulness, acceptability of CV Wizard; intent to use it; see	
perceptions	3.3.f.ii	
Maintenance over time	All measures over 2.5 years of follow-up, Arm 1; 1.5 years, Arm 2	
Potential covariates	Measurement	
Patient demographic	Age; gender; race / ethnicity; primary language; poverty level; insurance status at	

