#### **Quantitative Data**

To be included in Aim 1 analyses a patient must have at least one visit in the 6 months after the Arm 1 implementation date at an Arm 1 or Arm 2 CHC and at least one additional visit at a study clinic in the 12-month post-index visit period. The first visit is referred to as the index visit. We will describe those who had inadequate follow-up data (did not have at least one additional visit in the post-index period). For each study subject, CVD risk score / risk factor management status will be calculated at index visit and each encounter during follow-up. While the tool can be run for patients of any age, we will restrict our analyses to patients 40-75 years of age.

We will test for between-group differences in baseline characteristics such as age, sex, race and ethnicity, insurance type, visit count, and health status using chi-square, t-test, and nonparametric Wilcoxon rank-sum tests as appropriate. We will also test for association between baseline characteristics and our outcomes of interest. We will examine the number of patients seen in each service area and clinic and each Arm and compare the characteristics of Arm 1 patients for whom the tool was used to those in Arm 1 for whom the tool was not used and to Arm 2 patients. Because the two arms were selected based on clinic size, percent of patients with a diagnosis for hypertension and the percent of patients that use tobacco, we anticipate there will be differences between the two groups resulting in the need to adjust for these differences. We will also examine characteristics at the service area and clinic-level in Arm 1 for whom the tool was used compared to Arm 1 service areas / clinics for whom the tool was not used and Arm 2 service areas / clinics.

Unadjusted trends in the monthly use and view rates for each of the study CHCs will be explored with use rates defined as: the number of encounters where CV Wizard was printed / number of targeted encounters with high-CVD risk patients per month and view rates defined as the number of encounters where CV Wizard was viewed / number of targeted encounters with high-CV risk patients per month.

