## **Secondary Analyses**

Secondary analyses will examine use of the CV Wizard CDSS (main outcome). We will assess which patient-, encounter-, provider-, and clinic-level characteristics are associated with use of the CDS at eligible encounters. Additional analyses will explore the impact of CDS system use on prescribing pattens targeting CVD risk as well as the influence of system prioritization recommendations on risk factor management. We will also analyze results from a provider survey conducted to assess reasons for CV Wizard use and non-use.

Quantitative data will be derived from the CDS data repository and extracted EHR data. Provider survey data was collected from 44 study clinic clinicians conducted midway through the study period.

For quantitative analyses, descriptive statistics will show patient and encounter characteristics included in analyses. After exploring the distribution of the outcome variables to identify the most appropriate model, multilevel models with random effects for provider and clinic will be used to assess (1) multi-level characteristics associated with CV Wizard use and (2) the association between system use and system prioritization on CVD risk factor management.

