#### Additional Information about Sensitive Data

We plan to pull data related to mental health diagnoses (depression, anxiety, and severe mental illness) to determine whether it explains variance in CV Wizard tool use. This data will be pulled

from the EHR (i.e., this information will *not* be collected directly from patients that are participating in the qualitative interviews). We will follow the same safeguards for this sensitive data as we do for all data collected in this study (see sections on data management, sharing, and protection; confidentiality; and security). This data will be collected (as applicable) for all clinics participating in the study. Given that individual patients are not enrolled for this aim of the study, there is no consent form or PRA to which this information should be added. NOTE: Each OCHIN member clinic has business use agreements with OCHIN to handle and manage PHI from their clinical data, and each CHC agrees that their electronic health record data may be used in research as part of their membership agreement.

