### 9. Provisions to Monitor the Data to Ensure the Safety of Subjects

This study involves data from OCHIN, and through OCHIN, patient data from enrolled CHCs. The web service for CV Wizard© is hosted by Health Partners. All EHR data from OCHIN clinics are stored at OCHIN. Each clinic has business use agreements with OCHIN to handle and manage PHI from their clinical data. EHR data will be linked using OCHIN's unique patient identification codes, and data sources will be linked into a secure relational database at OCHIN. When data linkages have been completed, the data will be fully de-identified. Data analysis will be conducted at OCHIN. Deidentified, aggregate data will be shared with study team members from CHR and HealthPartners.

Yearly datasets will be created with data from CV Wizard's web server, imported into SAS, and securely maintained at OCHIN. Data will be extracted for all target patients seen in OCHIN study CHCs and stored (limited data set) in a Web-based secure repository. Data from subsequent encounters is stored and linked to the same patient. If necessary, to share PHI, we will use a secure data transfer website with access limited to appropriate members of the research team. IRB and HIPAA approval will be obtained for all study steps. CHR and OCHIN have expertise in high quality data management and project operations and multisite research collaborations. Data structures are typically designed to separate personal identifiers from other critical data, further enhancing protections. CHR, HealthPartners, and OCHIN standards meet or exceed requirements for patient data safety established in the federal HIPAA guidelines. Data structures will derive from the data confidentiality, security, and privacy standards that CHR/OCHIN/HealthPartners have in place to meet or exceed all current HIPAA requirements. These standards exceed Level 1 requirements, and meet the majority of Level 2 requirements, as specified by DHHS in its Automated Information Systems Security Handbook. All analyses will be carried out using SAS® version 9 or later. Quality control will begin with real-time, inter-field checks in the data at OCHIN. Additional back-end checks (for missing data and logical inconsistencies) will be conducted to ensure the highest standards of data reliability. We will examine the distribution and measurement properties of variables before making final decisions about analyses.

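### The tool-use model has random effects for provider and clinic but none for patient, so standard errors for largely fixed patient characteristics will be too small if a patient's encounters are correlated

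*Combined protocol and SAP*

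**What the plan says.** The Secondary Analyses section of the combined protocol and SAP sets the question: "We will assess which patient-, encounter-, provider-, and clinic-level characteristics are associated with use of the CDS at eligible encounters". The unit is therefore the encounter, as it is for the adoption measure under Secondary Outcome Measures, a percentage "of encounters where care team member opts to run the CV" Wizard risk assessment. The same section then fixes the clustering terms: "multilevel models with random effects for provider and clinic will be used". That sentence also covers a second model, relating system use and prioritization to risk factor management.

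Patients recur in these data. The Quantitative Data section admits a patient to the Aim 1 analyses only with an index visit and "at least one additional visit at a study clinic in the 12-month post-index visit period". It also plans to look at how the interval between visits relates to tool use in returning patients. The treatment-on-the-treated analysis separates patients with no use, one use and more than one use. Section 9 states: "Data from subsequent encounters is stored and linked to the same patient".

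Other models in the plan do handle this level. The intent-to-treat model has random effects for clinic and patient, and the Supplement's mixed models nest time within patients. For the tool-use model, no passage gives a patient random effect, a patient-clustered standard error, a GEE or a rule of one encounter per patient.

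**The concern.** Predictors at four levels are to be tested (patient, encounter, provider, clinic), but only two of those levels receive a random effect. Whether the tool is opened at one visit of a patient plausibly predicts whether it is opened at the next, even with the same provider and clinic. If so, a patient with four encounters supplies less than four encounters' worth of information about a trait such as race/ethnicity, yet the stated model counts all four in full.

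The question matters to this project. Its objective is to reduce disparities, and the section on sensitive data justifies extracting mental-health diagnoses "to determine whether it explains variance in CV Wizard tool use". A spurious finding that the tool is used less in some racial, income or diagnostic group could misdirect later implementation work.

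**Working it through.** **Plan's own figure.** The documents state no sample size, power, intraclass correlation or error rate for this model, so there is nothing to reproduce. The only alpha they give (0.05, two-sided) belongs to Supplement Aim 2b. It is assumed here.

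**Inputs, all assumed.** m is the number of encounters per patient (2, 4 or 8). ρ is the within-patient correlation of the 0/1 outcome, on the observed scale, that remains after provider and clinic. Neither is in the documents.

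**Step 1: formula.** Take a predictor that is constant within a patient and varies between the patients of a provider. The variance is understated by the design effect DE = 1 + (m − 1)ρ. The actual two-sided error of a nominal 5% test is 2 × [1 − Φ(1.96/√DE)].

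Worked case, m = 4 and ρ = 0.1: DE = 1 + 3 × 0.1 = 1.3; √1.3 = 1.140; 1.96/1.140 = 1.719; error = 8.6%.

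| m | ρ | DE | Actual error |
|---|---|---|---|
| 2 | 0.1 | 1.1 | 6.2% |
| 2 | 0.3 | 1.3 | 8.6% |
| 4 | 0.02 | 1.06 | 5.7% |
| 4 | 0.05 | 1.15 | 6.8% |
| 4 | 0.1 | 1.3 | 8.6% |
| 4 | 0.3 | 1.9 | 15.5% |
| 8 | 0.1 | 1.7 | 13.3% |
| 8 | 0.3 | 3.1 | 26.6% |

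At ρ = 0, DE = 1 and the error is 5% for any m.

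**Step 2: do the provider and clinic effects absorb the patient correlation?** This was simulated with 30 clinics, 3 providers per clinic, 15 patients per provider and 1,000 runs per setting. Binary use was generated on the logit scale with intercept −1 and standard deviations of 0.6 for clinic, 0.8 for provider and 0, 1.0 or 1.8 for patient. A patient-level predictor with no true effect was tested in a linear mixed model of the 0/1 outcome, with random effects for clinic and provider only.

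| m | No patient correlation | Lower correlation | Higher correlation |
|---|---|---|---|
| 2 | 4.0% | 6.8% (ρ about 0.13) | 10.0% (about 0.31) |
| 4 | 5.1% | 12.2% (about 0.13) | 15.8% (about 0.32) |
| 8 | 4.4% | 20.5% (about 0.14) | 29.5% (about 0.32) |

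The Monte Carlo standard error of a rejection rate is √[p(1 − p)/1000], for example 1.0 percentage point at 12.2% and 1.3 at 20.5%.

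**Step 3: compare the two.** At m = 4 and ρ = 0.132, DE = 1.396 and the formula gives 9.7%, against 12.2% simulated. At m = 4 and ρ = 0.319, DE = 1.957 and it gives 16.1%, against 15.8%. At m = 8 and ρ = 0.14, DE = 1.98 and it gives 16.4%, against 20.5%. So the simulation agrees in direction and rough size and is sometimes higher. One reason is that the simulated correlations are estimated slightly low: the estimate reads −0.037, −0.017 and −0.009 for m = 2, 4 and 8 when the true value is zero. Provider and clinic effects do not remove the inflation. The logit-scale patient correlations behind these runs are 0.23 and 0.50. They must not be put into the design-effect formula, which needs the observed-scale values.

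The simulation uses a linear rather than a logistic mixed model and equal numbers of encounters per patient. It did not test the remedy; the zero-correlation column shows only that the stated model holds its level when there is nothing to omit.

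**The case against.** The strongest reply is that the model is not final. The plan says "After exploring the distribution of the outcome variables to identify the most appropriate model", and Section 9 also defers final analysis decisions until variables have been examined. But both passages concern the distribution and measurement properties of variables. The clustering levels are stated outright, and nothing suggests that a patient level would be added.

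A second reply is that the effect may be negligible. That is possible: 2 encounters with correlation 0.05 give 5.6%, and 4 encounters with 0.02 give 5.7%. The documents cannot settle this.

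Several stronger readings are tempting but not supported:

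- That encounters count as fully independent. They share provider and clinic effects and are independent only given those.
- That every patient characteristic is affected alike. The Intent to Treat Analysis section provides for diabetes diagnosed during follow-up, and Table 6 lists insurance status at the visit. For predictors that change within a patient, the inflation is smaller and its direction is not guaranteed. The argument fits race/ethnicity best, and poverty level and chronic diagnoses largely.
- That the risk-factor-management model has the same fault. Its unit of analysis is not given, so the point reaches it only if it is fitted per encounter.
- That the trial's main result is at risk because tool use is labelled the main outcome. The label applies within the secondary analyses, and the intent-to-treat model already has a patient random effect.
- That false differences will be reported. They could be. This is an association analysis with no stated hypothesis or decision rule.

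**Conclusion.** The point holds as a defect in a stated secondary model. With repeat encounters, patient-level predictors and no patient term, the specification gives standard errors that are too small whenever positive within-patient correlation remains after provider and clinic. Confidence in the omission and its direction is high. Confidence in the size is limited, because both governing quantities are assumed. A fair summary for a fixed patient trait is about 6% actual error at the mild end (2 encounters, correlation 0.1), about 9% to 16% with 4 encounters and correlation 0.1 to 0.3, and from 13% upward with 8 encounters over the same range. The change should be made before the analysis is run, but the Aim 1 primary comparison does not depend on it.

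**What to change.** In Secondary Analyses, specify random effects for patient, provider and clinic, with patient crossed with provider where patients see several providers. State a fallback: if that model does not converge, keep the provider and clinic effects and report cluster-robust standard errors at clinic level with a small-sample correction. State the unit of analysis for the risk-factor-management model and apply the same rule if it is the encounter. Report the distribution of eligible encounters per patient and the estimated patient-level variance, so that readers can judge how much the term mattered.

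The linkage needed already exists. The cost is somewhat wider intervals, longer run time and possible convergence work, since a binary model with crossed effects and few encounters per patient can be hard to fit. Odds ratios also become patient-specific once the patient effect is added, and the report should say so. If the patient correlation is negligible, the added variance will estimate near zero and little is lost.

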#### **Supplement Addendum**

- (1) Descriptive Analyses (Aim 2a)
  - We will conduct a descriptive analysis on the following process outcomes: (1) Encounter patterns; (2) Rates of missed or cancelled appointments at in-person vs. VC (telephone, video) encounters; (3) Appointment wait times by encounter type, and (4) CV Wizard use (in encounters where there are CV Wizard CDS suggestions by encounter type.
  - We will use standard statistical tests (e.g., chi-square, t-tests) to describe measures in the periods pre- vs. post-COVID's onset.
- (2) Regression Analyses (Aim 2b)
  - Encounter is the unit of analysis.
  - We will assess associations between encounter type and: (1) Action taken on needed care plan components; (2) Up-to-date documentation of BP and A1c by 6 months postindex visit (accounting for whether BP data were taken in person or reported by the patient); and (3) Change in CVD risk factors by end of follow-up period. To do so, we will conduct adjusted regression analyses using longitudinal electronic health record data.

- To assess action taken on needed care, data for each factor will be extracted at each
  visit in the study period. We will use adjusted logistic regression models, with a
  dichotomous outcome of action taken or not taken.
- To assess *impact on individual CVD risk factors*, data for each factor will be extracted at index visit and all visits in the follow-up period (coded as controlled vs. not).
- Generalized linear mixed models (GLMM) with time nested within patients will be used to determine if risk factor control differs across encounter types, to estimate the effect of encounter type on change over time in CVD risk score and BP and A1c control. All encounters for each eligible patient will be included. CVD risk is influenced by factors amenable to clinical intervention (e.g., BP) and others that are irreversible (age); absent intervention, overall risk should increase with age. These analyses will be adjusted for or stratified by potential confounders at the patient, provider, and encounter level. This will include accounting for whether post-index visit encounters were in-person or VC, and the reason for the encounter, as in-person encounters in the post-COVID period may be for different reasons than VC encounters.
- To assess whether CV Wizard moderated the relationship between encounter type and CVD outcomes, we will also conduct these analyses using only encounters where CV Wizard alerted the user that there are CDS suggestions. We will compare outcomes between encounters where CV Wizard was used (viewed or printed out) vs. not used, by including its use as a variable in the models described above.
   Data on race / ethnicity and gender will be obtained for all study patients; analyses will adjust or stratify for them as indicated.

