### **Specific Aims**

**Aim 1.** Conduct a clinic-randomized trial of the impact of an evidence-based point-of-care CDS system on (i) overall CVD risk scores, and (ii) control of individual CVD risk factors (blood pressure; HbA1c, lipid levels; smoking; body mass index), among high CVD risk adult CHC patients.

**Aim 2.** Develop and hone need-based implementation support protocols to help Arm 1 CHCs implement the CV Wizard CDS system into their standard workflows; assess whether use of the protocols developed for Arm 1 CHCs accelerates implementation and adoption of the CDS system in the Arm 2 CHCs. **Supplement Addendum:** Compare CVD risk management in high-risk patients at in-person vs. virtual care (VC) encounters, in the periods pre- and post-COVID's onset.

**Aim 3.** Conduct a mixed methods process evaluation, guided by the Technology Acceptance Model (TAM), to identify and address patient, provider, and delivery system barriers to uptake/impact of this CDS in CHCs. **Supplement Addendum:** In a subset of study clinics, explore how CV Wizard's individualized, prioritized CVD risk summary is used in VC to guide care decisions and engage patients in shared decision-making.

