#### **Data Collection**

The mixed methods process evaluation will explore "what works, for whom and in what circumstances" related to CDS uptake, guided by our logic model and the Technology Acceptance Model (TAM). Our 3-tiered approach to data collection follows recent guidance on process evaluation of complex interventions which advocates complementing collecting key variables from all sites with in-depth data from purposively selected samples. This balances collecting data detailed enough to enable transferability (degree to which results can be applied to other contexts) and pragmatism (what is possible).

(1) All Clinics –We will collect the following information as it pertains to all clinics participating in the study: (1) baseline clinic data (e.g., location, patient characteristics, clinic characteristics, clinic size, etc.); (2) all 'trouble-tickets' relevant to CV Wizard submitted to OCHIN via its member help request system; (3) all user feedback submitted via CV Wizard's feedback mechanism; (4) all exchanges from the implementation support webinars; and (5) feedback from the practice facilitator and others involved with implementation support.

We will also collect attendee evaluations of all webinars. This pragmatic, adaptive approach will let us explore how to help diverse CHCs implement CDS, fine-tune materials and strategies for doing so, identify key barriers to adoption of CDS, and inform developing a guide for CHCs implementing CV Wizard.

SUPPLEMENT ADDENDUM		
Process outcomes	Description	
Encounter patterns	(i) Total clinical encounters; % in-person, by video, or by phone	
	(ii) % of patients whose encounters were all in-person, all VC, or a mix of	
	both	
	(iii) % encounters where CV Wizard alerts that there are CDS suggestions,	
	i.e., identified a target patient	
Missed / delayed	(i) % of scheduled appointments that are missed / cancelled, by encounter	
encounters	type	
	(ii) Appointment wait times (time from scheduling call to appointment), by	
	encounter type	
Tool use	% of encounters where care team member 'used' (viewed) suggested CV	
	Wizard CDS, by encounter type (among encounters occurring after CV	
	Wizard was activated at the clinic)	
Primary outcomes	Description	
CVD risk data up to	(i) % patients with up-to-date BP documented in EHR by 6 months post-	
date	index visit, and (ii) % patients with up-to-date A1c data documented in	
	EHR by 6 months post-index visit, by encounter type	

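### Aim 2a compares process measures before and after COVID onset with chi-square and t-tests that ignore clinic and patient clustering, so the p-values can err in either direction

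*Combined protocol and SAP*

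**What the plan says.** The supplement sets out to "Compare CVD risk management in high-risk patients at in-person vs. virtual care (VC) encounters, in the periods pre- and post-COVID's onset" (Specific Aims, Aim 2). Its first analysis block, Aim 2a in the Supplement Addendum of Section 7.a, opens with "We will conduct a descriptive analysis on the following process outcomes". It then lists encounter patterns, missed or cancelled appointments, wait times and CV Wizard use. The only inferential method named is: "We will use standard statistical tests (e.g., chi-square, t-tests) to describe measures in the periods pre- vs. post-COVID's onset".

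The process-outcomes table in Section 6.b shows the level of each measure:

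- Missed visits are counted per appointment: "i) % of scheduled appointments that are missed / cancelled, by encounter" type. Wait times are also per appointment.
- One encounter-pattern measure is per patient: "ii) % of patients whose encounters were all in-person, all VC, or a mix of" both.
- Tool use is per encounter and restricted by activation date: "Wizard CDS, by encounter type (among encounters occurring after CV" Wizard went live at the clinic.

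Other parts of Section 7.a do model the correlation. The intent-to-treat analysis has random effects for clinic and patient and a fixed effect for organization. Under Secondary Analyses, for CV Wizard use, "multilevel models with random effects for provider and clinic will be used". The Aim 2b mixed models nest time within patient. The statement "Encounter is the unit of analysis" stands under Aim 2b; Aim 2a gives no unit.

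**The concern.** Both periods draw on the study clinics, which are observed over time in one shared health record. Records from one clinic resemble each other, and a patient with several visits contributes several records, probably in both periods. A standard chi-square or two-sample t-test treats every record as a separate independent draw.

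Two kinds of dependence act in opposite directions. Stable differences between clinics or patients that appear in both periods cancel from the pre/post difference, so a test that ignores them overstates its standard error. Clinics that change by different amounts add variance that the test does not see, so it understates its standard error. For tool use, unequal change is likely by design: activation is staggered by 18 months between arms (Section 4), and clinics with low use receive extra support (Implementation Support, Section 6.b).

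At stake is how much confidence a reader can place in statements that missed visits, waits or tool use changed after COVID onset.

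**Working it through.** **The plan's own figure.** No alpha, sample size, power or ICC is stated for Aim 2a. The supplement's only figure is the Aim 2b power statement: 6000 per group, difference 5.0, SD 9.1 at both times, correlation 0.2, two-sided alpha 0.05. The SD of change is √(9.1² + 9.1² − 2×0.2×9.1×9.1) = 11.51, and power is 1.000, so the stated 100% reproduces. It has no bearing on the Aim 2a tests.

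**Inputs for Aim 2a.**
- ICC, the share of variance between clinics: not in the document; assumed 0.01 to 0.10.
- CAC, the correlation of a clinic's effect between periods: not in the document; assumed 0.5 to 1.0.
- m, encounters per clinic per period: not in the document; assumed 35 to 500. The Statistical Power section gives only more than 35 high-risk patients per clinic.

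**Formula.** Take J clinics, m encounters each per period, total variance 1, and encounters independent within a clinic-period.
- True variance of the pre/post difference: (2/J) × [ICC(1 − CAC) + (1 − ICC)/m]
- Variance the standard test uses: (2/J) × (1/m)
- Ratio: VR = (1 − ICC) + m × ICC × (1 − CAC). J cancels.
- Actual type I error at nominal 5%: 2 × [1 − Φ(1.96/√VR)]

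**Clinics shift alike (CAC = 1).** VR = 1 − ICC = 0.99, 0.95 or 0.90 for ICC 0.01, 0.05 or 0.10. Type I error is 4.9%, 4.4% or 3.9%, slightly conservative at any m.

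**Clinics shift by different amounts.** For ICC 0.05, CAC 0.8 and m = 200: VR = 0.95 + 200×0.05×0.2 = 2.95; 1.96/√2.95 = 1.14; type I error 25.4%.

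| ICC | CAC | m=35 | m=100 | m=200 | m=500 |
|---|---|---|---|---|---|
| 0.01 | 0.8 | 5.7% | 7.2% | 9.6% | 16.5% |
| 0.05 | 0.9 | 6.5% | 10.4% | 16.0% | 29.1% |
| 0.05 | 0.8 | 8.6% | 16.0% | 25.4% | 42.2% |
| 0.05 | 0.5 | 14.7% | 29.1% | 42.2% | 59.3% |
| 0.10 | 0.8 | 12.1% | 25.0% | 37.6% | 55.3% |

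**Simulation with repeat visits.** This used a binary outcome, 60 clinics, 35 patients per clinic, 3 encounters per patient per period and 2000 replicates. On the logit scale the intercept was −1.4, the clinic SD 0.5 and the patient SD 1.0. All values are assumed except the 60 clinics and the 35 patients, which follow the Statistical Power section.

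| Scenario | Pooled chi-square | Paired t-test on clinic differences |
|---|---|---|
| Same patients both periods, no clinic-by-period variation | 2.3% | 4.0% |
| Different patients, no clinic-by-period variation | 7.2% | 4.9% |
| Same patients, clinic-by-period SD 0.15 | 6.3% | 4.9% |
| Same patients, clinic-by-period SD 0.30 | 17.6% | 5.4% |
| As above, 100 patients per clinic | 34.5% | 4.8% |

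Repeat visits push the error down when the same patients are seen in both periods, and up when they recur only within a period. Respecting the clinic structure brings the test close to its nominal level in every scenario.

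**The case against.** The strongest reply is that Aim 2a is descriptive. It has no hypothesis, alpha, power or decision; the supplement's primary outcomes are listed separately, and Aim 2b analyses them with adjusted regressions and mixed models. That stands, and it limits the consequence. It does not make a p-value from an independence test valid, and the plan does intend to run such tests.

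Second, the wording is open. The tests are given as examples, a t-test can be paired or run on clinic rates, the plan already defines monthly use and view rates per CHC, and Section 9 defers final analysis decisions until distributions and measurement properties are examined. This is fair: the document does not prove that encounters will be pooled. But none of these places names a clustered or paired method for Aim 2a, and in standard form both named tests assume independence.

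Third, the sizes rest on assumed inputs, and patient overlap is inferred. Both are true. Nesting within clinics is enough for the point, but how large the error is, and in which direction, cannot be settled from the document.

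A reader might also infer that almost any period difference will test as significant, or that the effective sample is just the number of clinics. Neither is supported. No encounter counts are given, and at m = 35 with CAC 0.8 the error is only 5.7% to 8.6% for ICC 0.01 to 0.05. At ICC 0.05, CAC 0.8 and m = 200, the 60×200 = 12,000 encounters per period are worth about 12,000/2.95 ≈ 4,070 independent ones, far more than 60. Nor does seeing the same clinics and patients twice inflate significance by itself; alone, it makes these tests conservative.

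**Conclusion.** The point holds in limited form. The tests named for Aim 2a do not match nested, probably recurring data, and their p-values cannot be taken at face value. If clinics shift alike and patients recur, they are somewhat conservative, at about 2–5%. If clinics shift by different amounts they are anti-conservative, by an amount that grows with encounters per clinic. On the central assumptions (ICC 0.05, CAC 0.8) the error is about 9% to 42% over 35 to 500 encounters per clinic-period; with ICC 0.01 and the same CAC it is about 6% to 17%. All three inputs are assumptions.

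The consequence is confined to the descriptive statements about process measures. A reader might infer that the trial's primary comparison or the Aim 2b regressions share the fault. The document does not support this: those analyses use separate models, and the intent-to-treat models and the Aim 2b mixed models account for correlation explicitly.

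**What to change.** In the Aim 2a paragraph of Section 7.a, replace the chi-square and t-tests for the pre/post comparison with estimated period differences and cluster-robust confidence intervals. These can come from a GEE with clinic as the cluster, or from a mixed model with random clinic, random clinic-by-period and patient effects. The clinic-by-period term should be random; as a fixed effect it would leave no single period effect to report. State the unit of analysis for each measure. The simpler alternative is to report the estimates without p-values.

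Tool use needs separate wording. It counts only encounters after activation, so a clinic activated after COVID onset has no pre-period value and a post-minus-pre difference cannot be formed there. Either limit that comparison to clinics active in both periods, or adjust for activation timing and arm.

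The cost is a few lines of SAP text, minor programming with methods the plan already uses elsewhere, and usually wider intervals. No new data are needed.
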